3.0 DLQI/CDLQI 4-point improvement – additional analyses

Due to an unexpectedly low number of subjects with a baseline DLQI score ≥ 11 (adults) or baseline CDLQI score ≥ 13 (pediatric subjects), additional analyses will be made using the threshold of a baseline DLQI or CDLQI score ≥ 4 , ie. including in the analysis as many subjects as possible who have the possibility of obtaining a 4-point reduction. Except for the baseline threshold, the analyses will be performed as specified in the SAP Version 3.0, Section 5.4.2.

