1.3.2 Randomization Methodology

For the initial randomization in Period 1, up to 110 subjects are planned to be randomized in a 2:1 ratio to receive either TMB-001 0.05% or vehicle. Randomization will be stratified by age group (6-11 years, 12-16 years, ≥ 17 years), and genetic subtype (RXLI, ARCI). Randomization will be performed using a permuted block design with block sizes of 3 and 6 within each stratum.

For the randomization in Period 3, all subjects initially randomized to TMB-001 0.05% are planned to be randomized in a 1:1 ratio to receive either TMB-001 0.05% BID or QD. Up to 74 subjects can be randomized, based on their responder status, defined as having a ≥ 1 -point reduction in IGA score from Baseline at the Week 12 visit. No stratification factors are planned for this portion of the study. Randomization will be performed using a fixed block design with block sizes of 4.

Both randomizations will be performed centrally by 4G Clinical through their Interactive Response Technology (IRT).

The Optional Maximal Use arm is open-label and does not require randomization.

Full details can be found in the Randomization Plan.

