5.4 Patient-Reported Outcomes Analysis

All analyses in this section will be presented as described in Section 3.11.2, unless otherwise indicated. All analyses will be primarily performed using the ITT population, unless otherwise noted. No formal inference is intended to be performed on patient-reported outcomes.

5.4.1 IQoL-32 Responders at Week 12 and Week 24

The IQoL-32 contains 32 items, each scored from 0 to 4 ('not applicable', 'not at all', 'a little', 'a lot', 'tremendously') for a total score that varies between 0 and 128. The difference in proportions of subjects achieving an ≥ 11 -point change from baseline in IQoL-32 scores will be compared at Week 12 (between TMB-001 0.05% and vehicle treatment groups) and at Week 24 (between TMB-001 0.05% BID and QD maintenance dosing groups) computed based on the CMH method (stratified by CI type), along with 95% Wald confidence intervals. No imputation will be performed for missing Week 12 or Week 24 data. Results will be provided using the primary efficacy data presentation for the Week 12 analysis, and open-label dosing efficacy data presentation for the Week 24 analysis. Only subjects that are ≥ 16 years of age will be included in these analyses.

The Week 12 analysis will be repeated using the PP population. Additionally, the difference in proportions at Week 24 will be compared against Week 12, where 95% Wald confidence intervals will be provided.

Sensitivity analyses will be performed for both Week 12 and Week 24 analyses, where questions pertaining to areas of the body where TMB-001 is explicitly not administered (e.g., eyes, ears, and scalp) will be omitted. Questions 6, 7 and 14 of the IQoL-32 will

be removed from the analysis, and the total score for this sensitivity analysis will vary between 0 and 116.

5.4.2 DLQI/CDLQI Responders at Week 12 and Week 24

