The difference in proportions of subjects achieving an ≥ 4 -point change from baseline in DLQI/CDLQI scores will be compared separately for adult and pediatric subjects at Week 12 (between TMB-001 0.05% and vehicle treatment groups) and at Week 24 (between TMB-001 0.05% BID and QD maintenance dosing groups) computed based on the CMH method (stratified by CI type), along with 95% Wald confidence intervals. Adult subjects will be compared using the DLQI scores among adults with baseline scores of ≥ 11 , and pediatric patients will be compared using the CDLQI scores among pediatric subjects with baseline scores of ≥ 13 . No imputation will be performed for missing Week 12 or Week 24 data. Results will be provided using the primary efficacy data presentation for the Week 12 analysis, and open-label dosing efficacy data presentation for the Week 24 analysis.

Additionally, the difference in proportions at Week 24 will be compared against Week 12, where 95% Wald confidence intervals will be provided.

5.4.3 WI-NRS Responders at Week 24

The difference in proportions of subjects achieving a ≥ 4 -point improvement from baseline in weekly Worst Itch-QoL scores on the WI-NRS will be compared at Week 24, between the TMB-001 0.05% BID and QD maintenance dosing groups, computed in a similar manner as the primary efficacy endpoint using the CMH test, including the use of 50 multiply imputed datasets combined using the Wilson-Hilferty transformation for the pooled CMH statistic and Mantel-Haenszel stratum-weighted difference in proportions combined using Rubin's rule., along with 95% confidence intervals. Only subjects with baseline WI-NRS scores of ≥ 7 will be included in this analysis.

Unlike what is described in section 5.2.2.4, daily scores are not computed post-Week 12 visit, and so the difference in proportion at Week 24 will be computed using the results collected on Week 24, compared to baseline. In addition, the difference in proportions at Week 24 will be compared against Week 12, where 95% confidence intervals will be provided. Both analyses will be performed using multiply imputed data.

The analysis will be repeated using observed data only. The Mantel-Haenszel stratum-weighted estimator of the difference in proportion and the associated standard error will be used to produce a 95% confidence interval.

Results will be provided using the open-label dosing efficacy data presentation.

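### Wald intervals for the DLQI/CDLQI responder differences will cover less than 95% if the subsets, which the addendum calls unexpectedly low in number, hold about 30 subjects or fewer per comparison

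*SAP*

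**What the plan says.** SAP 5.4.2 defines a responder by a change of at least 4 points in DLQI or CDLQI. Response "will be compared separately for adult and pediatric subjects at Week 12" (TMB-001 against vehicle) and likewise at Week 24 (BID against QD). Adults enter only with a baseline DLQI of at least 11, pediatric subjects only with a baseline CDLQI of at least 13. The difference is CMH-based, stratified by ichthyosis type, and given "along with 95% Wald confidence intervals". Missing values shrink the subsets further: "No imputation will be performed for missing Week 12 or Week 24 data". The section also compares Week 24 with Week 12, again with Wald intervals.

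Addendum section 3.0 opens "Due to an unexpectedly low number of subjects with a baseline DLQI score" of at least 11, or CDLQI of at least 13. It adds analyses at a baseline score of at least 4 and then says: "Except for the baseline threshold, the analyses will be performed as specified in the SAP Version 3.0, Section 5.4.2". The Wald interval therefore carries over, and the original analyses are not withdrawn.

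SAP 5.4 adds: "No formal inference is intended to be performed on patient-reported outcomes". Protocol 10.3.1.1.3 asks only for 95% confidence intervals and names no method.

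**The concern.** The Wald interval for a difference in proportions takes its variance from the observed rates. In small arms those rates are often near or at 0 or 1, the estimated variance is then too small, and the interval covers less often than its label says. If every subject in each arm responds, or none does, its width is zero.

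The sponsor has recorded that these subsets are small and has left the interval unchanged. With no test planned, the interval is the main statement of uncertainty about the treatment difference on this patient-reported endpoint. One labelled 95% that covers in the 80s overstates what the data show. SAP 7.2 and 7.2.1 use exact binomial limits for single-group TEAE and LSR proportions, so small-sample intervals are not foreign to this plan.

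**Working it through.** **Inputs from the documents.** Interval, split, stratification and missing-data rule: SAP 5.4.2. Size: "up to 110 subjects are planned to be randomized in a 2:1 ratio" (SAP 1.3.2), and at most 74 subjects re-randomized 1:1 for Week 24, both before any baseline threshold.

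**Assumptions.** The documents give neither subset counts nor DLQI/CDLQI response rates. I took 2:1 splits from 6/3 upward (TMB-001/vehicle) and true rates of 50/10, 50/20, 60/30 and 70/10%. The first pair is the planning assumption for the primary IGA endpoint; the others are mine.

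**The plan's own figure.** The only stated size is 110 for the primary endpoint; it does no more than cap the subsets. With rates 0.5 and 0.1, ratio 2:1, two-sided alpha 0.01 and 90% power, the mean rate is (2 × 0.5 + 0.1)/3 = 0.367. The vehicle arm needs [2.576·√(1.5 × 0.367 × 0.633) + 1.282·√(0.25/2 + 0.09)]² / 0.4² ≈ 28, or 32 with continuity correction. That is 84 or 96 in total, and 84/0.85 ≈ 99 or 96/0.85 ≈ 113 after 15% dropout. The stated 110 lies between these.

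**Interval.** With observed rates p and q in arms of n and m, Wald is (p − q) ± 1.96·√[p(1−p)/n + q(1−q)/m]. Illustration with 4/8 against 0/4: the vehicle arm adds no variance, so the interval is 0.50 ± 1.96 × 0.177 = 0.15 to 0.85. Newcombe combines the Wilson limits of each arm (0.215 to 0.785; 0 to 0.490): lower 0.5 − √(0.285² + 0.490²) = −0.07, upper 0.5 + 0.285 = 0.78.

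**Exact coverage.** For each true pair, sum the binomial probabilities of all outcomes whose interval contains the true difference. Unstratified Wald, in %:

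| n/m | Four rate pairs | Mean over 10-90% grid | Grid minimum |
|---|---|---|---|
| 6/3 | 88-91 | 80.6 | 59.8 |
| 8/4 | 82-91 | 84.5 | 71.0 |
| 12/6 | 85-93 | 87.8 | 72.6 |
| 16/8 | 88-93 | 90.0 | 77.3 |
| 20/10 | 90-94 | 91.6 | 85.5 |
| 30/15 | 92-94 | 92.6 | 89.3 |
| 40/20 | 93-94 | 93.2 | 89.3 |

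For 1:1 allocation (Week 24), the grid mean is 85.7% at 5/5, 91.0% at 10/10 and 92.7% at 15/15.

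**Newcombe on the same four pairs.** It covers 93-96% from 8/4 upward; at 6/3 it falls to 91.3% at 70/10%. At 8/4 its mean width relative to Wald runs from 0.857/0.980, about 13% narrower (60/30%), to about 9% wider (70/10%).

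**Stratification.** Simulated with a Mantel-Haenszel difference over two strata at 50/10, 50/30, 70/50 and 80/20%. At 8/4 in total, coverage is 70.5-82.6% with the unpooled variance and 77.2-86.8% with the Sato variance. The unstratified interval on those same pairs covers 77.7-86.4%. Like for like, stratification therefore costs coverage with the unpooled variance and almost none with Sato. At 16/8 in total the ranges are 86.8-91.6% and 87.5-93.3%.

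**Zero width.** The probability is [pⁿ + (1−p)ⁿ]·[qᵐ + (1−q)ᵐ], with p and q now the true rates. At 6/3 and 70/10% this is (0.1176 + 0.0007) × (0.001 + 0.729) = 8.6%; over the four pairs it is 2-9%. The largest value is 3.8% at 8/4, 0.7% at 12/6 and 0.1% at 16/8.

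**The case against.** The strongest reply is that the subset size is unknown and the endpoint carries no decision. Both parts stand. A reader might infer that these intervals will certainly fall well short of 95%. The documents do not support that: they say the number was unexpectedly low, not what it was, and at 30/15 or 40/20 the shortfall is small. Some pairs do nearly as well earlier (50/10% at 16/8 gives 93.4%). Because the endpoint is descriptive, no type I error or success claim is touched.

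Other stronger readings also fail:

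- **That the sponsor split the subsets after seeing them.** The adult/pediatric split is already in SAP 3.0, and the addendum describes the low count in terms of those two groups.
- **That nothing else conveys uncertainty.** Addendum section 9.0 plots response rates with 95% intervals at both thresholds, and SAP 5.1 plans by-subject listings and plots.
- **That the threshold-4 analyses are equally affected.** They were added to enlarge the subsets, which eases the problem there; nothing says they are small.
- **That IQoL-32 (SAP 5.4.1) shares the fault.** It uses Wald intervals too, but has no baseline-score threshold and is not called small.
- **That zero-width intervals are a general risk.** They matter only near 6/3, where any interval would tell the reader little.

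It is also fair to say that the main coverage table is for an unstratified interval, while the SAP plans a stratified one without naming its variance. The stratified simulation does not remove the shortfall, but its size depends on that unstated choice.

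**Conclusion.** The point holds, conditionally. If a comparison has about 30 subjects or fewer, the planned interval is too optimistic: roughly 4 to 13 points short at 8/4 (95 − 91 to 95 − 82), 2 to 7 at 16/8 and 1 to 5 at 20/10 on the four rate pairs, and more over less favourable rates or with an unpooled stratified variance. At 45-60 subjects it is about 1-3 points short. These figures rest on assumed counts, assumed response rates and 2:1 allocation. The consequence is over-precise descriptive intervals, so this is a low-to-moderate priority correction, worth making because it is so cheap.

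**What to change.** In SAP 5.4.2, and through it the threshold-4 repeat in addendum section 3.0, replace the Wald interval for the between-arm differences at Week 12 and Week 24 with a stratified Newcombe or stratified Miettinen-Nurminen score interval. State what is reported when an arm or stratum is empty or all-or-none. The coverage figures above are for unstratified Newcombe; the stratified versions and Miettinen-Nurminen were not computed.

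Name a separate method for Week 24 versus Week 12. The same subjects may appear at both visits, so an independent-samples score interval may not suit it.

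Report the number of subjects per arm in each comparison beside the interval. IQoL-32 in 5.4.1 need not change, except for consistency.

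The cost is one SAP phrase and a standard software option, with no new data. Interval width moves by roughly −13% to +9% at 8/4.

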5.1.1 Estimand

The primary estimand is defined by the following:

- Population: Subjects in the ITT population as defined by protocol eligibility criteria.
- Variable: the proportion of subjects with a ≥ 2 -point improvement in the IGA score at Week 12 compared to baseline.
- The following intercurrent events and their handling include:
 - Treatment discontinuation prior to Week 12 due to adverse event or lack of efficacy: Composite variable strategy, where the discontinuation may be considered informative about the subject's outcome and will therefore consider these subjects as non-responders.
 - Modification to dose level: Treatment policy strategy, where results will be used regardless of dose modifications.
 - Use of prohibited medication: Composite variable strategy, where the use of such medication may be considered informative about the subject's outcome (e.g., subjects are using prohibited medications due to perceived lack of efficacy of study drug) and will therefore consider these subjects as non-responders.
- Population-level summary: The difference in proportions of subjects achieving IGA response at Week 12 between treatment groups (TMB-001 0.05% and vehicle).

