5.2.1 Estimands

The estimands of the key secondary endpoints can be written out in a similar manner as the estimand of the primary endpoint. High-level descriptions of estimands are outlined in the following table:

Table 1. Attributes of Estimands for Key Secondary Endpoints

Endpoint		
Difference in proportions of subjects with IGA-scores of clear/almost clear	Difference in proportions of subjects with ≥ 2 -point change IGA-scaling severity sub-scores	Difference in proportions of subjects with ≥ 4 -point improvement in worst Itch-QoL

Population	Subjects in the ITT population as defined by protocol eligibility criteria	Subjects in the ITT population as defined by protocol eligibility criteria	Subjects in the ITT population as defined by protocol eligibility criteria with baseline WI-NRS of ≥ 7
Variable	Proportion of IGA clear/almost clear score responders	Proportion of IGA-scaling sub-score responders	Proportion of worst Itch-QoL responders
Intercurrent Events and Strategies	1) Composite variable strategy for treatment discontinuations due to adverse event or lack of efficacy 2) Treatment policy strategy for dose modifications 3) Composite variable strategy for use of prohibited medications		
Population-level Summary	The difference in proportions of subjects achieving responses at Week 12 between the TMB-001 0.05% and vehicle treatment groups		

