5.3.2 Analysis Methods

All analyses in this section will be presented as described in Section 3.11.2, unless otherwise indicated. All analyses will be primarily performed using the ITT population, unless otherwise noted. No formal inference is intended to be performed on other secondary efficacy endpoints, however 95% confidence intervals will be provided. The estimand framework will be applied for all analyses using multiple imputation.

5.3.2.1 VIIS-Scaling Score 50% Reduction Responders at Week 12

The difference in proportions of subjects achieving at least a 50% reduction on average from baseline in VIIS-scaling score in all areas with baseline VIIS score ≥ 3 will be computed at Week 12 along with 95% confidence intervals, between the TMB-001 0.05% and vehicle treatment groups. The difference in proportions will be calculated in a similar manner as the primary efficacy endpoint using the CMH test, including the use of 50 multiply imputed datasets combined using the Wilson-Hilferty transformation for the pooled CMH statistic and Mantel-Haenszel stratum-weighted difference in proportions combined using Rubin's rule. Only the areas with baseline VIIS scores of ≥ 3 will be included in this analysis. Areas may include the upper back, the upper arm, the shin/lower leg, and the dorsal foot. Individual areas may reach a 50% reduction; however, subjects will be considered responders only if the average of all areas with baseline VIIS scores of ≥ 3 achieve a 50% reduction.

The analysis will be repeated using observed data only. The Mantel-Haenszel stratum-weighted estimator of the difference in proportion and the associated standard error will be used to produce a 95% confidence interval.

Results will be provided using the primary efficacy data presentation.

This analysis will be repeated using the PP population.

5.3.2.2 VIIS-Scaling Score 25% Reduction Responders at Week 12

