For completeness, a descriptive analysis of the I-NRS will also be provided, as applicable.

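### IQoL-32 and DLQI/CDLQI responders are analysed on observed scores with no stated estimand, so early stoppers without a score leave the denominator and the group difference can be biased in either direction

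*SAP*

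**What the plan says.** SAP 5.4.1 (IQoL-32) and 5.4.2 (DLQI/CDLQI) compare responder proportions by a CMH method stratified by CI type, with 95% Wald intervals, nominally in the ITT population. Both carry the sentence "No imputation will be performed for missing Week 12 or Week 24 data". Neither names an estimand or says how intercurrent events are handled. IQoL-32 has a per-protocol repeat at Week 12 and an item-omission analysis. DLQI/CDLQI has no sensitivity analysis. Addendum 3.0 repeats 5.4.2 with a lower baseline threshold and otherwise unchanged.

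The main responder endpoints are treated differently. For the primary endpoint, SAP 5.1.1 has "Treatment discontinuation prior to Week 12 due to adverse event or lack of efficacy: Composite variable strategy". It adds the same strategy for prohibited medication and in each case "will therefore consider these subjects as non-responders". Tables 1 and 2 of the SAP carry this over to the key and other secondary endpoints: "Composite variable strategy for treatment discontinuations due to adverse event or lack of efficacy". SAP 5.3.2 adds: "The estimand framework will be applied for all analyses using multiple imputation".

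Within the patient-reported section itself, Week 24 WI-NRS (5.4.3) is handled like the primary endpoint: "Both analyses will be performed using multiply imputed data". The whole section is non-inferential: "No formal inference is intended to be performed on patient-reported outcomes".

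**The concern.** Whether a subject has a Week 12 or Week 24 questionnaire is decided after randomisation and can depend on treatment. Restricting the analysis to those with a score conditions on that outcome. Subjects who stop because the ointment irritates the skin, or because it does not work, carry information about quality of life. Protocol 8.2.5 and 8.2.6 describe these instruments as picking up drug effects and contact dermatitis. If such subjects have no score, they are removed rather than counted as failures. If they used prohibited medication and do have a score, nothing in 5.4.1 or 5.4.2 stops them from counting as responders.

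At stake is the size of the reported quality-of-life difference and its comparability with the IGA, VIIS and itch results shown beside it. The plan offers no analysis from which a reader could see how much the missing scores matter.

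**Working it through.** **1. The plan's own figure.** The SAP gives no assumed rate or sample size for IQoL-32 or DLQI/CDLQI. The only related figures are those for the IGA primary endpoint (SAP 1.3.3): 50% vs 10%, 2:1, two-sided 1% level, about 90% power, about 15% dropouts and non-evaluable subjects, total 110. A normal-approximation calculation with continuity correction gives 32 on vehicle and 96 in total. Then 96 / (1 − 0.15) = 113, within 3% of 110. The point does not depend on this; it supplies the 50%, 10% and 15% used below.

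**2. Who leaves the denominator.** Protocol Table 1 schedules both questionnaires at Baseline, Week 12 and the end-of-study/early-termination visit only. SAP 3.10 lets an in-person unscheduled visit stand in for Week 12 if it falls within 14 days of the target day. I found no rule that maps an earlier termination questionnaire onto Week 12. Protocol 2.2 reports that most local skin reactions in Phase IIb occurred at Weeks 2 and 4. A subject who stops then would usually have no Week 12 score. A subject who stops treatment but is scored in the window stays in at the observed value.

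**3. Formula.** Let pA and pV be the response rates among subjects with a score. Let dA and dV be the shares who stop for an adverse event or lack of efficacy and have no score.

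- Observed-score difference = pA − pV
- Composite difference = pA(1 − dA) − pV(1 − dV)
- Overstatement = pA·dA − pV·dV

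**4. Results for Week 12.** All rates and losses by arm are assumptions. Each loss pattern averages 15% at 2:1 allocation: (2×15 + 15)/3, (2×20 + 5)/3 and (2×10 + 25)/3. Entries are the composite difference in points, with the overstatement by the observed-score analysis in brackets.

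| Rates, active vs vehicle | Observed | Loss 15%/15% | Loss 20%/5% | Loss 10%/25% |
|---|---|---|---|---|
| 50% vs 10% | 40.0 | 34.0 (+6.0) | 30.5 (+9.5) | 37.5 (+2.5) |
| 50% vs 30% | 20.0 | 17.0 (+3.0) | 11.5 (+8.5) | 22.5 (−2.5) |
| 50% vs 40% | 10.0 | 8.5 (+1.5) | 2.0 (+8.0) | 15.0 (−5.0) |

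For example, the first cell is 0.50 × 0.85 − 0.10 × 0.85 = 0.425 − 0.085 = 0.34.

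The 15% in the SAP covers all dropouts and non-evaluable subjects, so assigning all of it to adverse events and lack of efficacy is generous. With half of it (7.5% in each arm) at 50% vs 10%, the overstatement is 0.50 × 0.075 − 0.10 × 0.075 = 0.03, or 3 points.

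**5. Direction.** The observed-score analysis favours TMB-001 only if pA·dA > pV·dV, that is, if dV/dA is below pA/pV. The limits are 5.0 (50% vs 10%), 1.67 (50% vs 30%) and 1.25 (50% vs 40%). Beyond them the sign reverses. At 50% vs 10% with 5%/30% loss, the composite difference is 40.5 against 40.0 observed.

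**6. Week 24.** The planned comparison is BID against QD among re-randomised subjects. The same formula applies with those two groups, and the error favours whichever regimen loses more would-be failures in the sense of step 5.

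**7. Scale against precision.** Addendum 3.0 says that fewer subjects than expected met the DLQI/CDLQI baseline thresholds but gives no count. Assuming 20 vs 10 subjects at 50% vs 30%, the 95% Wald half-width is 1.96 × √(0.25/20 + 0.21/10) = 36 points. With 74 vs 36 it is 1.96 × √(0.25/74 + 0.21/36) = 19 points.

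**The case against.** **Direction.** A reader might infer that this rule makes the drug look better. The documents do not support that. The composite event includes lack of efficacy, which could be more frequent on vehicle. Dropout is not split by arm or reason. The Phase IIb summary gives no discontinuation rates and calls most skin reactions mild or moderate. Protocol 7.1 handles reactions by interruption in the affected areas and asks sites to keep subjects in the study. This stands. At Week 24 a bias towards TMB-001 has no meaning, because both groups receive it.

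**Silence.** A reader might also take it as settled that the composite rule is excluded. A composite rule is not imputation, so a ban on imputation does not rule it out. The sentence linking the framework to multiple imputation sits in 5.3.2 and does not expressly govern 5.4. Addendum 9.0 plots these questionnaires with the estimand framework as far as it applies. The handling is therefore ambiguous, not clearly wrong. But the ambiguity is itself a fault, since a table and a figure could report different rates for one endpoint.

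**Scope.** It would be too strong to call these completer-only analyses, because stoppers with an in-window score are kept. It would also be too broad to say that every other responder analysis has the rule. Week 24 WI-NRS has it only by reference to the primary method, and for the average-itch scale the SAP says "For completeness, a descriptive analysis of the I-NRS will also be provided, as applicable".

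**Comparability.** Completer or observed-data repeats are planned for the primary, key secondary and most other secondary endpoints, so like-for-like comparisons can be made. True, but there they supplement a main analysis; here observed data are the only analysis.

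**Consequence.** These outcomes are untested and outside the hierarchy, and the shifts in most scenarios are small beside the likely interval widths. This stands and limits the weight of the point.

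**Conclusion.** The gap is real. For IQoL-32 and DLQI/CDLQI, and for the addendum 3.0 repeat, the only handling of missing scores is to leave them out. No estimand is stated and no analysis shows the effect. This departs from the composite rule that the SAP sets for its primary, key secondary and other secondary responder endpoints.

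Across the nine scenarios in the table, the error at Week 12 runs from +9.5 to −5.0 points, with 6 points at 50% vs 10% and equal 15% loss. These figures assume the response rates, the loss by arm, that all of that loss is for an adverse event or lack of efficacy, and that none of those subjects has an in-window score. Confidence is high that the rule is missing and that stoppers without a score leave the denominator. The direction cannot be settled from the documents. Because the outcomes are non-inferential, this is a worthwhile low-cost improvement and does not threaten the trial's main conclusions.

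**What to change.** In SAP 5.4.1 and 5.4.2 and in addendum 3.0, state an estimand with the 5.1.1 strategies. Subjects who stop for an adverse event or lack of efficacy, or use prohibited medication, before the time point stay in the denominator as non-responders. Table 2 of the SAP already does this for Week 24 endpoints. Dose modification stays under treatment policy. Say how scores missing for other reasons are handled; the present no-imputation rule can stay for those. Keep the observed-score analysis as supplementary, and make addendum 9.0 use the same rule so that tables and figures agree.

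One matter must be settled first. Protocol Table 7 lists bland emollients and low-potency hydrocortisone among prohibited products, while protocol 6.5 and 7.1 allow their use in some circumstances. These passages must be reconciled before use of these products is counted as failure.

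The cost is a short text change, reruns of the Week 12, Week 24, per-protocol, item-omission and addendum outputs, and slightly lower reported response rates. SAP 5.1.2 already summarises intercurrent events by type and treatment group for the primary endpoint, so much of the information needed is already being compiled.
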